
Test Product, Dose, and Mode of Administration:
 
CUTAQUIG, human normal immunoglobulin for subcutaneous (SC) administration.
 
CUTAQUIG will be administered by SC infusion every week (± 2 days, Cohort 1 and Cohort 2), every other week (± 2 days, Cohort 3) at the doubled weekly dose. The dosing frequency will be determined by cohort assignment.
 
Patients will receive the same mg/kg body weight dose as their previous SCIG product prior to study entry.
 
If, during the study, a patient's body weight changes by $>5\%$ from the first infusion of IMP, the dose will be adjusted to keep a constant mg/kg body weight basis. Additional adjustments will be made by the Investigator at study visits if the patient's body weight changes $>5\%$ from the previous adjusted weight.
 
Each patient's CUTAQUIG dose may be individualized, if considered necessary by the Investigator, by titrating upward or downward.
 
Batch (lot) numbers will be reported in the final report of the study.

Duration of Treatment:
 
Individual patient participation will be approximately 30 to 32 weeks:
 
• Screening Period: 1 to 2 weeks*• Stabilization Period: 4 weeks**• CUTAQUIG Treatment Period: 24 weeks (6 months)• Termination Visit: 1 week after last CUTAQUIG infusion for Cohort 1 and Cohort 2; 2-weeks after last CUTAQUIG infusion for Cohort 3

Name of Sponsor/Company: Octapharma USA, [name]	
Name of Investigational Product: CUTAQUIG	Protocol Identification Code: SCGAM-06
Name of Active Ingredient: Human Normal Immunoglobulin	Date of Final Protocol: 28-Aug-2019

* Patients entering the study established on weekly SCIG infusions will have a 1-week (± 2 days) Screening Period. Patients entering the study established on every other week dosing will have a 2-week (± 2 days) Screening Period.

** Patients entering the study currently active and established on CUTAQUIG in Study SCGAM-03 will skip Stabilization Period.

Reference Therapy, Dose, Mode of Administration:

Not applicable.

Study Outcome Parameters (Primary and Secondary Endpoints):**Primary Endpoint Parameters:**

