9.2.2 Efficacy Analysis Plan

The rate of SBI per person-year (bacterial pneumonia, bacteremia/sepsis, osteomyelitis/septic arthritis, visceral abscess, bacterial meningitis) during the CUTAQUIG treatment period will be presented as point estimates of the rate along with a 99% CI. Calculation of this confidence interval will account for intra-patient correlation in incidents following a compound Poisson process model. Furthermore, all observed SBIs will be listed individually and in full detail.

The duration of infection will be summarized by standard descriptive statistics by type of infection and by severity. The individual characteristics of each infection, including the time to resolution will be listed.

The use of antibiotics will be reported as a detailed list of all such medications, and the number of patients treated with antibiotics, the number of treatment episodes and the number of treatment days will be tabulated.

The US FDA Guidance for Industry on Safety, Efficacy, and Pharmacokinetic Studies to Support Marketing of Immune Globulin Intravenous (Human) as Replacement Therapy for Primary Humoral Immunodeficiency suggests that, based on historical data, a statistical demonstration of a serious bacterial infection rate per person-year less than 1.0 is adequate to provide substantial evidence of efficacy.^[25] Therefore, this background information will be used for a descriptive evaluation of the serious bacterial infection rate in this study as described above. Exploratory statistical testing may be performed if considered appropriate.

The QoL data will be presented descriptively by visit, along with the change from Baseline, defined as the Treatment Period Baseline Visit.

For Cohort 3, the change in total IgG trough levels when switching from weekly to every other week infusions will be tested confirmatory by means of a one-sided, paired t-test at the $\alpha=0.025$ level of significance. The following pair of hypotheses will be tested:

$$H_a: T_{eow} > T_w - 1 \quad \text{vs.} \quad H_0: T_{eow} \leq T_w - 1$$

where T_{eow} is the mean total IgG trough on steady-state dosing every other week, T_w is the same for weekly dosing, and a maximum decrease of 1 g/L for the mean total IgG trough level is considered acceptable.

T_w will be determined after completion of the Stabilization Period, T_{eow} at the final study visit.

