7.4. Derived and Computed Variables

The following derived and computed variables have been initially identified as important for the analysis of the primary and secondary target variables. It is expected that additional variables will be required. The SAP will not be amended for additional variables that are not related to the primary target or key secondary target variables. Any additional derived or computed variables will be 090-SAP-SCGAM-06-clean version3.0_13FEB2022

identified and documented in the SAS programs that create the analysis files. If the SAP is not amended, further derivations related to primary and secondary target variables will be described in the CSR.

- **Age** will be derived according to the usual definition that a person is n years old until she or he has completed her or his $(n+1)^{\text{th}}$ year of life, using the date of informed consent as the reference date. This is also the definition that will be applied for evaluation of the age related inclusion criteria [Unit: years]
- **Body Mass Index:** $\text{BMI} = (\text{Body weight}) / \text{Height}^2$ [Unit: kg/m^2]
- The **CUTAQUIG stabilization period** is defined for patients that did not participate in the SCGAM-03 trial as the period between the day of first treatment with study drug to the end of the observation period. This will usually be the treatment period baseline visit.
- The **CUTAQUIG treatment period** is defined as the period between the day of first treatment with study drug in a modified dosing regimen to the end of the observation period. For patients that previously completed the SCGAM-03 trial, this is also the period of first treatment with the SCGAM-06 study drug. The end of the observation period will usually be the termination visit.
- The **rate of serious bacterial infections** per year during regularly repeated treatment with CUTAQUIG will be calculated as $r = (\text{Total number of serious bacterial infections occurring in the stabilization and treatment periods}) / (\text{Sum of stabilization and treatment periods})$ [Unit: 1/years]
- The **rate of other infections** will be derived using the same method

Calculation of the confidence intervals of these rates will account for intra-patient correlation in incidents following a compound Poisson process model.[1]

With C_i infections for the i^{th} patient, and C total infections, the adjusted 2-sided 98% CI is calculated by:

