8.4. Measurement of Treatment Compliance

The following parameters will be listed and summarized per patient and/or per infusion:

- Body weight
- Actual dose (total and per kg body weight, based on the latest available weight measurement)
- Total dose of CUTAQUIG administered
- Total number of infusions administered
- Total volume of solution administered
- Infusion times
- Overall amount of product administered (only included in data listings)
- Maximal volume administered (in total and per kg body weight)
- Injection sites
- Injection flow rates

Deviations from the planned treatment schedule will be examined by summarizing the number of patients with infusions, and the number of infusions, that deviate from the scheduled intervals by more than 2 days, and by listing all cases with more than two days deviation individually. The number of patients with infusions, and the number of infusions with an incorrect dose administered will also be summarized.

Study drug exposure will be summarized by planned volume (mL), volume infused (mL), CUTAQUIG dose administered (mg), and CUTAQUIG dose administered by baseline body weight (mg/kg).

9. Efficacy Analysis

The rate of SBI per person-year (bacterial pneumonia, bacteremia/sepsis, osteomyelitis/septic arthritis, visceral abscess, bacterial meningitis) during treatment with CUTAQUIG will be summarized descriptively and a two-sided 98% CI will be presented. Calculation of this CI will account for intra-patient correlation in incidents following a compound Poisson process model. This analysis will also include summaries of the number of patients with any SBI, the number of SBIs, and the duration of treatment (annualized). Furthermore, all observed SBIs will be listed individually and in full detail.

Infections will be analyzed in the same manner as SBIs, except the analysis will be presented by Stabilization Group and Treatment Group separately. Further, the duration of infection will be summarized by severity. The individual characteristics of each infection, including the time to resolution will be listed.

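### SAP 7.4 pools stabilization and treatment time in the SBI rate, whereas Protocol 9.2.2 sets that rate for the treatment period, which starts with the modified regimen

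*SAP*

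**What the plan says.** Protocol 9.2.2 presents the SBI rate per person-year "during the CUTAQUIG treatment period will be presented as point estimates of the rate along with a 99% CI". The protocol's Study Outline (Duration of Treatment) has a line "Stabilization Period: 4 weeks" and, apart from it, a 24-week Treatment Period. The protocol glossary ties the Treatment Period to the parameters of the assigned cohort.

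SAP 7.4 uses the same term in the same sense: the CUTAQUIG treatment period is the "period between the day of first treatment with study drug in a modified dosing regimen to the end of the observation period". Within the same section, the numerator of the SBI rate is the "Total number of serious bacterial infections occurring in the stabilization and treatment periods" and the denominator is the "Sum of stabilization and treatment periods".

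SAP section 9 describes the SBI rate only as a rate during treatment with the product, and then adds: "Infections will be analyzed in the same manner as SBIs, except the analysis will be presented by Stabilization Group and Treatment Group separately".

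Protocol 3.1.2 and SAP 3.2.2 both list SBI occurrence among the variables that evaluate safety and efficacy under the three infusion parameters.

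**The concern.** The SAP formula departs from the protocol's stated period and from the SAP's own definition of that period, and the SAP gives no reason. Under Protocol 3.2 and 3.3.2, stabilization infusions are weekly, at the dose and flow rate of the previous product. That time is not exposure to larger site volumes, faster rates or every-other-week dosing.

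At stake is which question the main SBI figure answers. A reader who takes it as the rate under the modified regimens would be reading a figure that includes exposure before the switch. With few or no SBIs, the upper limit depends almost entirely on person-time, so the added weeks tighten it without adding information on the new regimens. This matters most in Cohort 3, where the interval between doses doubles at Treatment Period Baseline. In addition, patients who come directly from SCGAM-03 skip stabilization (Protocol 6.1.2), so the pooled denominator is not built the same way for every patient.

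**Working it through.** **Inputs.** Stabilization 4 weeks and treatment 24 weeks, with Termination 1 week after the last infusion in Cohorts 1 and 2 and 2 weeks after it in Cohort 3 (Study Outline). Planned numbers 15, 15 and 35 (Protocol 9.1). Zero-event upper limit from the SAP 7.4 code: half the 0.99 chi-square quantile on 2 degrees of freedom, divided by person-years. One year is taken as 52.18 weeks. Full follow-up and no direct SCGAM-03 entrants are assumed at first.

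**The plan's own figures.** 4 + 24 = 28 weeks, which matches the approximate total treatment time in SAP 4.1. The standard normal 0.99 quantile is 2.326, which matches the SAP's multiplier of 2.33 for a 98% interval. The zero-event constant is 4.605.

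**Stabilization share of pooled time.** Baseline to Termination is 24 + 1 = 25 weeks (Cohorts 1 and 2) or 24 + 2 = 26 weeks (Cohort 3).
- Cohorts 1 and 2: 4/29 = 13.8%.
- Cohort 3: 4/30 = 13.3%.
- All 65 patients: treatment time is 30 × 25 + 35 × 26 = 1,660 patient-weeks and stabilization is 65 × 4 = 260, so the share is 260/1,920 = 13.5%.

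**Zero SBIs: 98% upper limit = 4.605 / person-years.**

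| Group | Treatment Period only | Pooled (SAP 7.4) |
|---|---|---|
| Cohort 1 or 2, n=15 | 15×25/52.18 = 7.19 PY; 0.64 | 15×29/52.18 = 8.34 PY; 0.55 |
| Cohort 3, n=35 | 35×26/52.18 = 17.44 PY; 0.26 | 35×30/52.18 = 20.12 PY; 0.23 |
| All 65 | 1,660/52.18 = 31.81 PY; 0.145 | 1,920/52.18 = 36.80 PY; 0.125 |

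**With events.** Let s be the stabilization share and k the SBI rate in stabilization divided by the rate in treatment. Then pooled rate / Treatment Period rate = 1 − s + s·k. With s = 0.135:
- k = 0 (all SBIs after the switch): 0.865, so the pooled rate is about 14% low (25/29 = 0.862 for Cohorts 1 and 2; 26/30 = 0.867 for Cohort 3).
- k = 0.5: 0.93.
- k = 1: 1.00, no change.
- k = 2: 1.135, so the pooled rate is about 14% high.

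Example: one SBI in the Treatment Period among 65 patients gives 1/31.81 = 0.031 per person-year, or 1/36.80 = 0.027 pooled. The SAP's upper limits are these rates times e^2.33, which is 0.32 and 0.28.

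**Direct SCGAM-03 entrants.** Their number is not given. If 25% or 50% of patients skipped stabilization (assumed), the share for all 65 would fall from 13.5% to 10.5% or 7.3%.

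**The case against.** The strongest reply is that the pooled rate has a purpose. One secondary objective is simply to gather more safety and efficacy data on CUTAQUIG. Protocol 7.2 counts SBIs per person-year on treatment throughout the study, and the SAP labels its rate as one for repeated treatment with the product, not for the modified regimens. Pooling also counts every SBI from the first dose. This stands as a reason to keep a pooled rate. It does not explain why that rate replaces the one Protocol 9.2.2 names.

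Some stronger readings are tempting, and the documents do not support them:

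- *Pooling makes the SBI rate look better.* A reader might infer this as a fact, but for the point estimate it depends on k. Excluding patients with active infection around Screening (Protocol 4.1.2) makes a lower rate in stabilization plausible but does not establish it.
- *The SAP explicitly exempts SBIs from the split by period.* The sentence in SAP section 9 at most implies this. It speaks of infections, and the listed secondary variable covers infections of any kind or seriousness, so the split may include SBIs. SAP 7.4 points the other way: it names a rate of other infections and gives it the same method as the SBI rate. The text is ambiguous.
- *Stabilization time says nothing about the modified regimens.* For infection protection this is too strong in Cohorts 1 and 2, whose planned weekly mg/kg dose does not change at the switch. Even in Cohort 3, an IgG half-life of about 30 to 35 days (Protocol 1.1) means that the change at Baseline is not sharp.
- *A cluster of SBIs after the switch would be hidden.* Both documents require a detailed listing of each SBI, and the SAP also tabulates SBIs and the patients who have them.

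**Conclusion.** The mismatch is real and changes reported figures, but its size is modest. With full follow-up and no direct SCGAM-03 entrants, stabilization is 13% to 14% of pooled person-time. The zero-event upper limit is then always too small as a limit for the Treatment Period, by the amounts in the table. With events, the point estimate is too low only when SBIs are rarer in stabilization than in treatment, by 13% to 14% if all of them fall in the Treatment Period.

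A reader might infer that the departure decides whether the rate passes the 1.0 per person-year benchmark. In the zero-event case it does not: the largest Treatment Period limit is 0.64. SBI is a secondary endpoint, and Protocol 9.2.2 uses the benchmark descriptively. A reader might also infer a material imbalance between cohorts. Without direct entrants the shares are 13.8% and 13.3%, and the documents give no numbers of direct entrants from which a larger gap could be shown. What remains is a departure from the protocol's stated period that should be corrected before analysis, chiefly for Cohort 3.

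**What to change.** In SAP 7.4 and section 9, make the Treatment Period SBI rate and its interval the main result, by cohort and overall, as Protocol 9.2.2 states. Count events and person-years from the first modified-regimen infusion to Termination. Show SBIs and person-time in stabilization separately, as section 9 already plans for infections, and keep the pooled rate as a labelled supplementary result. If the sponsor prefers pooling as the main result, the SAP should state the departure from the protocol and justify it.

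Two wordings should be settled in the same edit. One is whether the by-period infection analysis in section 9 includes SBIs, and how it fits with the same-method statement for other infections in SAP 7.4. The other is the SAP definition of stabilization, which covers only patients who did not take part in SCGAM-03. Former SCGAM-03 patients who moved to a commercial product must also complete stabilization (Protocol 6.1.2).

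The cost is a changed definition and some added table rows, with no new data. The upper limits become slightly less favourable. The confidence level (99% in the protocol, 98% in the SAP) is a separate matter; the figures here use the SAP's 98%.

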On the other hand, local reactions at SC injection sites are common. These reactions are rarely severe and are accepted by most patients. In the meta-analysis by Orange et al the reporting rate varied from 0.028 to 0.697 per infusion demonstrating that the majority of patients tolerate SCIG well.[3]

CUTAQUIG, the investigational medicinal product (IMP) in this study, is an immunoglobulin preparation from human normal plasma and is manufactured by Octapharma. It contains 16.5% (165 mg/mL) protein. The product is formulated for SC infusion by pump or syringe.

A recent study of 61 patients who were previously treated with IVIG received a total of 64 weekly SCIG infusions of CUTAQUIG (equating to 3,497 total infusions of CUTAQUIG); no serious bacterial infections developed among any patients during the study. The rate of other infections per person-year during the primary observation period was 3.43 (upper 95% CI: 4.57).^[4]

CUTAQUIG was approved by the US FDA in December 2018 for the treatment of primary humoral immunodeficiency in adults. Further information on the IMP can be found in the Investigator's Brochure and the US FDA-approved Package Insert.^[5]

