9.2 Statistical Analysis

All data collected will be listed and presented descriptively in full detail, by cohort as well as in total, to facilitate comparison between the different dosing regimens.

As detailed in Section 9.1, the change in total IgG trough levels when switching from weekly to bi-weekly infusions will be tested in Cohort 3 by means of a one-sided, paired t-test at the $\alpha=0.025$ level of significance.

Descriptive summaries will be presented for each of the primary and secondary variables according to their individual data types. The results of this study will be presented at the descriptive level only; any additional p-value or confidence interval presented is to be understood in the exploratory sense.

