3.2.2. Secondary Target Variables

Secondary assessment criteria will evaluate quality of life, along with additional evaluations of CUTAQUIG safety and efficacy being administered according to 3 different infusion parameters.

These will be assessed using the following variables:

- QoL assessments using the Short Form Health SurveySF-36 or SF-10
- Occurrence of serious bacterial infections (SBIs)
- Annual rate of all infections of any kind or seriousness
- Time to resolution of infections
- Use of antibiotics (number of days and annual rate)
- Individual profiles of IgG trough levels over time (all cohorts)

- Vital signs (blood pressure, pulse, body temperature, respiratory rate)

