7.2. Withdrawals

Patients who withdraw from the study prematurely will be considered in all data presentations for which they contribute data; in particular for the analysis of annual rates they will be considered with their actual observation periods.

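### The interval for the rate of other infections uses an uncentred sum of squared patient counts, so it is too wide even with no intra-patient correlation

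*SAP*

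**What the plan says.** SAP section 7.4 defines the SBI rate r as total events over total observation time and says that the rate of other infections "will be derived using the same method". On the intervals it states: "Calculation of the confidence intervals of these rates will account for intra-patient correlation in incidents following a compound Poisson process model". With C_i the infections of patient i and C their total, "and C total infections, the adjusted 2-sided 98% CI is calculated by"

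exp( ln r ± 2.33 · sqrt(ΣC_i² / C²) ).

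Nothing is subtracted from C_i, and follow-up time enters only through r. A separate chi-square limit covers the case of zero events.

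SAP section 9 carries the method over to infections in general: "Infections will be analyzed in the same manner as SBIs, except the analysis will be presented by Stabilization Group and Treatment Group separately". SAP section 3.2.2 lists as a secondary variable "Annual rate of all infections of any kind or seriousness". SAP section 7.2 says of patients who withdraw early that "in particular for the analysis of annual rates they will be considered with their actual observation periods".

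**The concern.** The formula treats each patient as a cluster and takes ΣC_i² as the variance of C. That is the variance of a compound Poisson total. If the number of event-bearing clusters is Poisson with mean λ and the cluster size is X, then Var(C) = λ·E[X²], which ΣC_i² estimates without centring.

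This suits SBIs, where few patients have any event. It does not suit all infections, where most patients have at least one and the number of patients is fixed by enrolment. Then Var(C) = ΣVar(C_i), and ΣC_i² estimates that plus the sum of the squared means.

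At stake is the interval for a named secondary endpoint. It will be printed as a 98% interval that allows for intra-patient correlation, although part of its width reflects only how common infections are. The rate would look less precise than the data support, overall and by cohort.

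**Working it through.** **Inputs.**
- Rate of other infections: 3.43 per person-year in the earlier study of this product; 2 to 5.18 across published studies (Protocol 1.1). These are assumptions for the present trial.
- SBI rate: 0 to 0.09 per patient-year (Protocol 1.1).
- Follow-up: 4 weeks of Stabilization and 24 weeks of Treatment (Protocol 6.2.1). One year is taken as 52.18 weeks.
- Patients: about 65, with at least 15, 15 and 35 by cohort (SAP section 5).
- Between-patient variation: not given in the documents. I write Var(C_i) = m + k·m², where m is the mean count per patient, and show k = 0, 0.5, 1 and 1.5.

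**The plan's own figures.** The 99th normal percentile is 2.326, so 2.33 is right for a two-sided 98% interval. The zero-event limit, half of the chi-square 0.99 quantile on 2 df, is 4.605 = −ln(0.01), also right. Only the variance is at fault.

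**Closed form, equal follow-up.**
- SAP variance of ln r, in expectation: N(m + k·m² + m²)/(N·m)² = (1/m + k + 1)/N.
- Correct variance: N(m + k·m²)/(N·m)² = (1/m + k)/N.
- Ratio of standard errors: sqrt(1 + m/(1 + k·m)).

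The excess variance is 1/N, whatever m and k are.

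**Numbers at 3.43 per year.** The mean count is m = 3.43 × 24/52.18 = 1.58 for Treatment, 1.84 over 28 weeks and 0.26 for the 4-week Stabilization Period. With independent Poisson counts, 1 − exp(−1.58) = 79% of patients would have at least one infection during Treatment.

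| Standard error, SAP / correct | k = 0 | 0.5 | 1 | 1.5 |
|---|---|---|---|---|
| Treatment, 24 weeks | 1.61 | 1.37 | 1.27 | 1.21 |
| Both periods, 28 weeks | 1.69 | 1.40 | 1.28 | 1.22 |
| Stabilization, 4 weeks | 1.12 | | | 1.09 |

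Over 2 to 5.18 per year at 24 weeks the ratio is 1.39 to 1.84 at k = 0, and 1.18 to 1.23 at k = 1.5. Simulation agrees with the closed form within about 0.01 for N = 65 at 24 and 28 weeks. With 10% early withdrawal the simulated ratios are unchanged (1.60 to 1.22).

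**Typical 98% interval, N = 65, 24 weeks** (1/m = 0.634):
- k = 0, SAP: SE = sqrt(1.634/65) = 0.1585, interval 2.37 to 4.96. Centred, t = 2.386: SE = sqrt(0.634/65) = 0.0988, interval 2.71 to 4.34.
- k = 1.5, SAP: SE = sqrt(3.134/65) = 0.2196, interval 2.06 to 5.72. Centred: SE = sqrt(2.134/65) = 0.1812, interval 2.23 to 5.28.

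**Simulated coverage of the nominal 98% interval, SAP formula, N = 65, 24 weeks:** 100.0, 99.8, 99.6 and 99.2% for k = 0 to 1.5.

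**A bound that needs no k.** Since ΣC_i² ≥ C²/N, the SAP standard error can never fall below 1/sqrt(N). The limits are therefore never closer to r than a factor exp(2.33/sqrt(N)): 1.34 for N = 65, 1.48 for N = 35 and 1.82 for N = 15. If all 65 patients had exactly two infections over equal follow-up, the SAP standard error would still be 1/sqrt(65) = 0.124.

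**SBIs.** At 0.09 per year over 28 weeks, m = 0.048 and sqrt(1.048) = 1.02.

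**Can k be pinned down?** The earlier study reported 3.43 with an upper 95% limit of 4.57, in 61 patients and 3,497 weekly infusions (about 67.0 person-years, m = 3.77). From ln(4.57/3.43) = 0.287, N × variance is 61 × (0.287/1.96)² = 1.31, or 1.86 with 1.645. Subtracting 1/m = 0.27 gives k = 1.0 or 1.6 if that limit used a centred variance. Subtracting a further 1 gives 0.0 or 0.6 if it used the SAP's formula. The protocol does not say which, so k from 0 to about 1.6 is compatible.

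**The case against.** The algebra is not in dispute; the weight is. The endpoint is secondary, no threshold or hypothesis attaches to it, and Protocol 9.2 says "any additional p-value or confidence interval presented is to be understood in the exploratory sense". The error is conservative. All of this stands and sets the priority.

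The largest ratios need k = 0, meaning that every patient shares one infection rate. In a mixed primary immunodeficiency population aged 2 to 75 that is unlikely. At k of 1 to 1.5 the Treatment Period ratio is about 1.2 to 1.3. The 28-week figures may not match any planned table, since infections are to be shown by period. Both points are fair. The lower bound also does harm only when the correct standard error lies below it, that is when 1/m + k < 1; at m = 1.58 this needs k < 0.37. The bound shows that the formula is wrong in kind, not how wide the interval will be in practice.

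The correction is also imperfect. With the t quantile and N = 65 it covers 97.8% at k = 1 and 97.5% at k = 1.5. With N = 15 and k = 1.5 it covers 97.4%, against 98.6% for the SAP formula. At k = 2, outside the range above, the figures are 96.8% and 97.9%. In the 15-patient cohorts the gain is therefore small at high dispersion. In the 4-week period there is none: at k = 0, 1.12 × 2.33 is already about 2.62, the t quantile.

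A footnote calling the interval conservative would be honest, but the 98% label would remain wrong for the overall and Cohort 3 Treatment Period rates, where the correction works well.

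**Conclusion.** The point holds. For the rate of other infections the SAP's variance is wrong by 1/N, because a fixed number of patients is treated as a random number of clusters. In the 24-week Treatment Period at 3.43 per year the standard error is 1.2 to 1.6 times too large for k between 1.5 and 0, and the 98% interval covers 99.2% to 100.0% with 65 patients. Over 2 to 5.18 per year the factor runs from 1.18 to 1.84.

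The direction does not depend on k; the size does, and the documents give no k. The figures rest on infection rates from earlier studies, gamma-Poisson counts and, except in the withdrawal check, equal follow-up. Rate estimates, the SBI interval in practice, and the confirmatory Cohort 3 trough test are unaffected. It is worth correcting, at low priority.

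**What to change.** In SAP section 7.4, for the rate of other (or all) infections only:
- replace ΣC_i²/C² with [N/(N−1)] · Σ(C_i − r·t_i)² / C², where t_i is the patient's actual observation time in the period analysed, in line with SAP section 7.2;
- replace 2.33 with the 0.99 quantile of t on N − 1 degrees of freedom: 2.39 for N = 65, 2.44 for N = 35, 2.62 for N = 15.

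Keep the present formula for SBIs and the chi-square rule for any cell with no events. State in section 9 that the two kinds of rate use different variances, and why.

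The t quantile is part of the fix. At N = 15 over 24 weeks the centred variance with 2.33 covers only 96.8, 96.3, 96.0 and 95.4% (k = 0 to 1.5). With t it covers 98.2, 97.8, 97.6 and 97.4%. A plain Poisson interval is not a safe substitute: at N = 65 over 24 weeks it covers 92.5% at k = 0.5 and 86.3% at k = 1.

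The cost is one formula, one quantile and a few lines of SAS, using counts and follow-up times already collected. The price is slight under-coverage in the 15-patient cohorts if dispersion is high.
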